7.11.3 Outliers

All values will be included in the analyses.

7.11.4 Visit Windows

The acceptable time ranges of the efficacy and safety examinations, observations, etc. from the date of initial study treatment (Day 1) are defined as follows. If there are multiple data available over the same period of time, the data obtained on the day closest to the reference date will be utilized; the later date will be applied if the number of days from the reference date is equal. Missing data at the end or discontinuation of treatment will be imputed using the LOCF method.

Since the study period of this study differs depending on the subject, the timing for the required visits to the study center will also differ from subject to subject. Only subjects who transferred from study RAJ1, but not those who transferred from studies RAJ3 or RAJ4, are required to come for visits at Week 2, Week 4, Week 8, Week 16, Week 20, Week 28, Week 32, Week 40, and Week 44. Therefore, these time points defined in the analysis are set only for the subjects from study RAJ1.

7.11.5 Handling of Schedule of Assessments of Efficacy Variables

For data obtained after the end of treatment, the data obtained within +2 days after the last dose will be included in analysis, except for the data at the end of the study (at time of follow-up).

(1) RA disease activity (TJC, SJC, PGA, SGA, subject's assessment of pain), CRP, ESR

Time points defined in analysis	Reference date*	Acceptable time range
Week 0	Day 1	Day 1
Week 2	Day 15	Day 12 to Day 18
Week 4	Day 29	Day 22 to Day 36
Week 8	Day 57	Day 50 to Day 64
Week 12	Day 85	Day 78 to Day 92
Week 16	Day 113	Day 106 to Day 120
Week 20	Day 141	Day 134 to Day 148
Week 24	Day 169	Day 162 to Day 176
Week 28	Day 197	Day 190 to Day 204
Week 32	Day 225	Day 218 to Day 232
Week 36	Day 253	Day 246 to Day 260
Week 40	Day 281	Day 274 to Day 288
Week 44	Day 309	Day 302 to Day 316
Week 48	Day 337	Day 330 to Day 344
Week 60	Day 421	Day 407 to Day 435
Week 72	Day 505	Day 491 to Day 519
Week 84	Day 589	Day 575 to Day 603
Week 96	Day 673	Day 659 to Day 687
Week 108	Day 757	Day 743 to Day 771
Week 120	Day 841	Day 827 to Day 855
Week 132	Day 925	Day 911 to Day 939
Week 132 + 12 × x	Day $7 \times (132 + 12 \times x) +$	Day $7 \times (132 + 12 \times x) - 13$ to
	1	Day $7 \times (132 + 12 \times x) + 15$
End/discontinuation of treatment	Day of the last dose	Day 2 to 2 days after the last dose
End of the study	28 days after the last	21 to 25 days after the last dage
(at time of follow-up)	dose	21 to 35 days after the last dose

^{*:} Day 1 represents the first day of study treatment.

(2) Patient Questionnaires (HAQ-DI, FACIT-Fatigue)

The schedule for FACIT-Fatigue applies only to subjects who transferred from study RAJ1.

Time points defined in analysis	Reference date*	Acceptable time range
Week 0	Day 1	Day 1
Week 2	Day 15	Day 12 to Day 18
Week 4	Day 29	Day 22 to Day 36
Week 8	Day 57	Day 50 to Day 64
Week 12	Day 85	Day 78 to Day 92
Week 16	Day 113	Day 106 to Day 120
Week 20	Day 141	Day 134 to Day 148
Week 24	Day 169	Day 162 to Day 176
Week 28	Day 197	Day 190 to Day 204
Week 32	Day 225	Day 218 to Day 232
Week 36	Day 253	Day 246 to Day 260
Week 40	Day 281	Day 274 to Day 288
Week 44	Day 309	Day 302 to Day 316
Week 48	Day 337	Day 330 to Day 344
Week 60	Day 421	Day 407 to Day 435
Week 72	Day 505	Day 491 to Day 519
Week 84	Day 589	Day 575 to Day 603
Week 96	Day 673	Day 659 to Day 687
Week 108	Day 757	Day 743 to Day 771
Week 120	Day 841	Day 827 to Day 855
Week 132	Day 925	Day 911 to Day 939
Week 132 + 12 × x	Day $7 \times (132 + 12 \times x) +$	Day $7 \times (132 + 12 \times x) - 13$ to
	1	Day $7 \times (132 + 12 \times x) + 15$
End/discontinuation of treatment	Day of the last dose	Day 2 to 2 days after the last dose
End of the study	28 days after the last	21 to 35 days after the last dose
(at time of follow-up)**	dose	21 to 33 days after the last dose

^{*:} Day 1 represents the first day of study treatment.

^{**:} The assessment at the end of the study (at the time of follow-up) will be scheduled only for HAQ-DI.

(3) Patient Questionnaires (SF-36v2®)

Time points defined in analysis	Reference date*	Acceptable time range
Week 0	Day 1	Day 1
Week 4**	Day 29	Day 22 to Day 36
Week 8**	Day 57	Day 50 to Day 64
Week 12**	Day 85	Day 78 to Day 92
Week 16**	Day 113	Day 106 to Day 120
Week 20**	Day 141	Day 134 to Day 148
Week 24	Day 169	Day 162 to Day 176
Week 28**	Day 197	Day 190 to Day 204
Week 32**	Day 225	Day 218 to Day 232
Week 36**	Day 253	Day 246 to Day 260
Week 40**	Day 281	Day 274 to Day 288
Week 44**	Day 309	Day 302 to Day 316
Week 48	Day 337	Day 330 to Day 344
Week 60**	Day 421	Day 407 to Day 435
Week 72	Day 505	Day 491 to Day 519
Week 84**	Day 589	Day 575 to Day 603
Week 96	Day 673	Day 659 to Day 687
Week 108**	Day 757	Day 743 to Day 771
Week 120	Day 841	Day 827 to Day 855
Wash 120 + 12 ×**	Day $7 \times (120 + 12 \times x) +$	Day $7 \times (120 + 12 \times x) - 13$ to
Week 120 + 12 × x**	1	Day $7 \times (120 + 12 \times x) + 15$
End/discontinuation of treatment	Day of the last dose	Day 2 to 2 days after the last dose

^{*:} Day 1 represents the first day of study treatment.

(4) Patient Questionnaires (WPAI [subjects from RAJ3 or RAJ4])

Scheduled only for subjects who transferred from studies RAJ3 or RAJ4.

Time points defined in analysis	Reference date*	Acceptable time range
Week 0	Day 1	Day 1
Week 24	Day 169	Day 162 to Day 176
Week 48	Day 337	Day 330 to Day 344
Week 72	Day 505	Day 491 to Day 519
Week 96	Day 673	Day 659 to Day 687
Week 120	Day 841	Day 827 to Day 855
Week 120 + 24 × x	Day $7 \times (120 + 24 \times x) +$	Day $7 \times (120 + 24 \times x) - 13$ to
	1	Day $7 \times (120 + 24 \times x) + 15$
End/discontinuation of treatment	Day of the last dose	Day 2 to 2 days after the last dose

^{*:} Day 1 represents the first day of study treatment.

^{**:} Scheduled only for subjects who transferred from study RAJ1. For subjects who transferred from studies RAJ3 or RAJ4, the survey is administered every 24 weeks after Week 120. Starting at the first visit after the revision of the study protocol, the survey will be administered to subjects who transferred from study RAJ1 also every 24 weeks.

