[Subjects who transferred from studies RAJ3 or RAJ4] Chest radiography is taken at the Week 0 visit, or data obtained within 28 days prior to the Week 0 visit may be used.  
If a respiratory AE is observed, a chest radiography may be taken at any time as necessary, even in an unscheduled visit.
- m. Blood samples for pharmacodynamics (lymphocyte subset assay) are collected before the first dose of the study drug on the day of the Week 0 visit.
- n. Assessment of disease activity: **Physician** – TJC (68 joints), SJC (66 joints), PGA (VAS); **Subject** – SGA (VAS), subject's assessment of pain (VAS), HAQ-DI, WPAI, and SF-36V2®.
- o. SF-36v2® is administered every 4 weeks until Week 48 and every 24 weeks after Week 48 to subjects from study RAJ1 and every 24 weeks throughout the study period to subjects from studies RAJ3 or RAJ4.
- p. WPAI is administered only to subjects who transferred from studies RAJ3 or RAJ4.
- q. AEs must be collected from the time of the administration of the first dose of study drug to the end of all assessments at the end of study (at time of follow-up).

- CONFIDENTIAL -

- r. After all of the assessments and tests scheduled for Week 0 have been completed, the subjects will receive the first dose of the study drug at each study center.
- s. [Subjects who transferred from study RAJ1] If the study is terminated before the Week 48 visit, the specified date for the study visit at the end of treatment will be the date of the previous visit + 28 days (allowable range,  $\pm 7$  days). If the study is terminated in or after the Week 48 visit, the specified date for the study visit at the end of treatment will be the date of the previous visit + 84 days (allowable range,  $\pm 14$  days).  
[Subjects who transferred from studies RAJ3 or RAJ4] The specified date for the study visit at the end of treatment will be the date of previous study visit + 84 days (allowable range,  $\pm 14$  days).
- t. For unscheduled visits, these assessments and tests should be performed only if clinically indicated as determined by the investigator.
- u. In principle, the subject should visit the study center on the specified date. If it is not possible for subjects to visit the study center on the specified date, the date of the visit should be adjusted to the date closest to the reference date as possible.
- v. Only subjects who transferred from study RAJ1 should make study visits at Weeks 2, 4, 8, 16, 20, 28, 32, 40, and 44.

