### 5.3.1.8 Patient Reported Outcomes/Assessments

Subjects will complete the following questionnaires according to Table 1, Schedule of Assessments. The answers written in the questionnaire will be recorded in the eCRF.

- HAQ-DI [Fries et al, 1982; Ramey et al, 1992]
- SF-36v2® [Ware, 2004]
- WPAI [Takeuchi T, 2011; Reilly MC, 1993] (WPAI is only administered to subjects who transferred from studies RAJ3 or RAJ4)

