Allowable range from specified date	-	±3	±7	±7	±7	±7	±7	±7	±7	±7	±7	±7	±7	±7	±7	±14	±14	±14	±14	±14	±14	- p	±7	
Assessment																								
FACIT-Fatigue, SF-36 ®	X		X	X	X	X	X	X	X	X	X	X	X	X	X	X	X	X	X	X	X	X		X q
HAQ-DI	X*	X	X	X	X	X	X	X	X	X	X	X	X	X	X	X	X	X	X	X	X	X	X	X q
Assessment of AEs and SAEs n	X	→																			X	X	X	
Confirm study drug prescriptions/ remaining drug residues o	X	X	X	X	X	X	X	X	X	X	X	X	X	X	X	X	X	X	X	X	X	X		
Record concomitant medications and therapies	X	X	X	X	X	X	X	X	X	X	X	X	X	X	X	X	X	X	X	X	X	X	X	X

- a. Be sure to obtain informed consent before beginning any of the procedures involved in the study. In principle, informed consent should be obtained at the Week 12 visit in study RAJ1.
- b. Assessments and tests performed at Week 0 should be performed on the same day as the Week 16 at end of study (day of follow-up) in study RAJ1. For items marked with the \* symbol, the results of the assessments and tests performed at Week 16/end of study (at time of follow-up) in study RAJ1 may be used.
- c. From the time of the Week 48 visit onward, the subject should be contacted once a month to confirm the status of compliance with study drug dosing and the safety of the subject. Moreover, because this study will end at the point in time where the Phase III Study begins, the duration of the treatment period will differ depending upon the subject. Accordingly, the timing for the required visits to the study center will also differ from subject to subject. When administration of the study drug has ended, the assessments and tests scheduled to be performed at end of treatment and end of study (at time of follow-up) will be performed.
- d. The assessments and tests to be performed at end of treatment should be performed promptly after administration of the study drug has ended. If administration of the study drug has been terminated early, the assessments and tests specified to be performed at end of treatment/early termination should

- CONFIDENTIAL -

be performed within 2 days of the last dose of the study drug if possible. Moreover, even subjects who have had early termination during the scheduled treatment period should in principle visit the study center at end of study (at time of follow-up).

- e. The assessments and tests scheduled for end of study (at time of follow-up) should be performed 28 days after the visit at end of treatment.

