- m. Assessment of disease activity: **Physician** – TJC (68 joints), SJC (66 joints), PGA (VAS); **Subject** – SGA (VAS), subject's assessment of pain (VAS), Health Assessment Questionnaire – Disease Index (HAQ-DI), FACIT-Fatigue, and SF-36®.
- n. AEs must be collected from the time of the administration of the first dose of study drug to the end of all assessments at end of study (at time of follow-up).
- o. After all of the assessments and tests scheduled for Week 0 have been completed, the subjects will receive the first dose of the study drug at each study center.
- p. If the study is terminated before the Week 48 visit, the specified date for the study visit at end of treatment will be the date of the previous study visit + 28 days (allowable range  $\pm 7$  days). If the study is terminated in or after the Week 48 visit, the specified date for the study visit at end of treatment will be the date of the previous visit  $\pm 84$  days (allowable range  $\pm 14$  days).
- q. For unscheduled visits, these assessments and tests should be performed only if clinically indicated as determined by the investigator.
- r. In principle, the subject should visit the study center on the specified date. If it is not possible for subjects to visit the study center on the specified date, the date of the visit should be adjusted to the date closest to the reference date as possible.

( GPF 2.02 )

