10.4.3	Raw value and change from baseline of preceding study in DAS28 score at each interval Influence of Dose Escalation	X					X	Subjects Who Experienced Dose Up to 150 mg
10.5	Raw value and change from baseline of preceding study in DAS28 score at each visit subgroup analysis Study Region (Japan, Korea, Taiwan)	Х	Х			Х		preceding studies

12-Nov-2019 Astellas Page 62 of 94

Analysis Type/Analysis Variable		Compone	ent for use		Study for	r Analysis		Amalusia Guana
Analysis 1	ype/Analysis Variable	CRP	ESR	None	RAJ1	RAJ3	RAJ4	Analysis Group
10.6	Raw value and change from baseline of preceding study in DAS28 score at each visit Mean-standard deviation plot	X	X		X	X	X	preceding studies
10.7.1	Raw value and change from baseline of preceding study in DAS28 score at each visit Mean-standard deviation plot Analysis by Treatment Sequence Set of preceding study	X			X			Treatment Sequence Set
10.7.2	Raw value and change from baseline of preceding study in DAS28 score at each visit Mean-standard deviation plot Analysis by Treatment Sequence Set of preceding study	Х				X		Treatment Sequence Set
10.7.3	Raw value and change from baseline of preceding study in DAS28 score at each visit Mean-standard deviation plot Analysis by Treatment Sequence Set of preceding study	X					X	Treatment Sequence Set
11	Raw value and change from baseline of preceding study in SDAI score at each visit	Х			X	X	X	preceding studies
12	Raw value and change from baseline of preceding study in CDAI score at each visit			Х	X	X	X	preceding studies
13	Raw value and change from baseline of preceding study in HAQ-DI at each visit			X	Х	X	X	preceding studies

12-Nov-2019 Astellas Page 63 of 94

		Compon	ent for use		Study fo	r Analysis		
Analysis T	ype/Analysis Variable	CRP	ESR	None	RAJ1	RAJ3	RAJ4	Analysis Group
14	Raw value and change from baseline of preceding study in FACIT-Fatigue at each visit			X	X			RAJ1
15	Raw value and change from baseline of preceding study in WPAI at each visit			X		X	X	RAJ3 and RAJ4
16	Raw value and change from baseline of preceding study in SF-36v2 at each visit			X	X	X	X	preceding studies
17	Raw value and change from baseline of preceding study in TJC68 at each visit			X	X	X	X	preceding studies
18	Raw value and change from baseline of preceding study in TJC28 at each visit			X	X	X	X	preceding studies
19	Raw value and change from baseline of preceding study in SJC66 at each visit			X	X	X	X	preceding studies

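### FACIT-Fatigue is missing from the current visit schedule but keeps an end-of-treatment analysis row; if collection stopped after ver. 1.3, that row would show a questionnaire that may be years old

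*SAP*

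**What the plan says.** **Where FACIT-Fatigue is kept.** Protocol 2.3.2 lists the FACIT-Fatigue score as an efficacy variable for subjects from RAJ1. Protocol 7.8.1(2) and SAP 7.11.5(2) place it in one window table with HAQ-DI. The SAP adds that "The schedule for FACIT-Fatigue applies only to subjects who transferred from study RAJ1". A footnote to that table removes only the follow-up time point for FACIT, so the End/discontinuation row stands, with an acceptable range of "Day 2 to 2 days after the last dose". SAP Appendix 1, item 14, plans "Raw value and change from baseline of preceding study in FACIT-Fatigue at each visit". Protocol 8.1.2 still names FACIT-Fatigue among the questionnaires kept as source records.

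**Where it is absent.** Protocol 5.3.1.8 says "Subjects will complete the following questionnaires according to Table 1, Schedule of Assessments", and the list that follows holds HAQ-DI, SF-36v2 and WPAI only. The current Table 1 has no FACIT row, and the questionnaires named in its note n are "HAQ-DI, WPAI, and SF-36V2". The schedule and note n in SAP section 2 omit FACIT as well, and so does the list of baseline disease-activity variables in SAP 7.2.2.2.

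**Where it used to be.** The ver. 1.3 excerpt in Protocol Appendix 7 has a schedule row headed "FACIT-Fatigue, SF-36", marked from Week 0 and Week 4 onward through end of treatment, and its footnote names "HAQ-DI), FACIT-Fatigue, and SF-36".

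**Imputation.** SAP 7.11.4 (and Protocol 7.8) states: "Missing data at the end or discontinuation of treatment will be imputed using the LOCF method". It sets no limit on the age of the value and makes no exception for FACIT.

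**The concern.** A reader of the clinical study report will take an end-of-treatment FACIT row as fatigue after long-term treatment. If the questionnaire was no longer given after ver. 1.3, the row would instead show two things at once: current values for subjects who stopped while FACIT was still scheduled, and old values for those who went on. If FACIT left the schedule with ver. 2.0/3.0, the old values come from the period when the ver. 1.3 doses of 50 and 100 mg applied. They would miss any later change of dose or loss of response. The row would sit beside HAQ-DI and SF-36v2 results that are still scheduled at end of treatment, so patient-reported outcomes under one label would refer to different times.

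**Working it through.** **Step 1: is FACIT in the current schedule?** Appendix 7 is superseded text, so its difference from the current Table 1 is not itself an error. It shows only that FACIT once had scheduled visits, including end of treatment. The conflict lies within the current documents: Protocol Table 1, note n and 5.3.1.8 and the SAP schedule leave FACIT out, while Protocol 2.3.2, 7.8.1(2) and 8.1.2 and SAP 7.11.5(2) and Appendix 1 keep it in. For SF-36v2, both documents explain how the frequency changed for RAJ1 subjects after the protocol revision. FACIT has no such note.

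**Step 2: which value does the end-of-treatment row select?** The reference date is the day of the last dose. The window opens on Day 2 and closes 2 days after the last dose. SAP 7.11.4 takes the value closest to the reference date when several fall in one window. Any on-treatment FACIT after Day 1 therefore qualifies, and the latest one is used whatever its age. The LOCF sentence leads to the same value. SAP 7.11.2 names LOCF at end of treatment only for ACR, DAS28 and safety data and treats FACIT at item level, so LOCF for FACIT rests on the general sentence in 7.11.4. Because the window alone selects the old value, removing LOCF would not cure the problem.

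**Step 3: how old could that value be?** The plan states no figure to reproduce. Inputs:
- Visit day = 7 × week + 1. For Week 132 this gives 925, as tabulated. Week 96 gives 673 and Week 48 gives 337.
- Days of exposure = months × 30.4375 (the SAP 6.5 conversion).
- Week 132 is the planned maximum duration of treatment in ver. 1.3. SAP 7.3.1 tabulates exposure in bands up to and beyond 84 months.
- The week of the last FACIT is an assumption, because the documents do not date its removal.

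Age in years = (months × 30.4375 − visit day of last FACIT) / 365.25.

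- 36 months, last FACIT at Week 132: (1095.75 − 925) / 365.25 = 0.47
- 36 months, last FACIT at Week 48: (1095.75 − 337) / 365.25 = 2.08
- 84 months, last FACIT at Week 132: (2556.75 − 925) / 365.25 = 4.47
- 84 months, last FACIT at Week 48: (2556.75 − 337) / 365.25 = 6.08

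| Exposure (months) | Last FACIT Week 132 | Week 96 | Week 48 |
|---|---|---|---|
| 36 | 0.5 y | 1.2 y | 2.1 y |
| 48 | 1.5 y | 2.2 y | 3.1 y |
| 60 | 2.5 y | 3.2 y | 4.1 y |
| 72 | 3.5 y | 4.2 y | 5.1 y |
| 84 | 4.5 y | 5.2 y | 6.1 y |

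**Step 4: how many subjects?** Only RAJ1 subjects have FACIT. The sample-size rationale (Protocol 7.1, SAP 4) puts 201 of them in this extension. That is a ceiling: it includes those who stopped before the schedule changed, and the number who continued is not given.

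**The case against.** The strongest objection is that nothing in the documents says collection stopped. FACIT is still an endpoint. Its window table limits it to RAJ1 subjects and removes the follow-up point, which suggests that its time points were considered when the study was opened to RAJ3 and RAJ4. Protocol 8.1.2 lists it beside WPAI, which is not in the ver. 1.3 schedule. A missing row is also weak evidence alone: the pain VAS has no row of its own in Table 1, yet it is assessed at every visit. This stands as far as it goes. A reader might infer that FACIT was certainly discontinued; the documents support only an unresolved contradiction. The pain VAS parallel is incomplete, though, because pain is named in note n and in Protocol 5.3.1.2, whereas FACIT is in neither note n nor 5.3.1.8.

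It is also fair that the by-visit rows use narrow windows and cannot carry an old value forward, that SAP 7.1 reports n for every continuous summary, so a small late-visit n beside a large end-of-treatment n would be visible, and that Appendix 1 rules out hypothesis testing. These points limit the harm to one row, but they do not tell the reader how old its values are.

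**Conclusion.** The point holds conditionally. As written, the plan contradicts itself on whether FACIT-Fatigue is collected under the current protocol. If it is not, following the stated rules gives an end-of-treatment row that mixes current values with values about 0.5 to 2.1 years old at 36 months of exposure and 4.5 to 6.1 years old at 84 months. This rests on the last FACIT falling between Week 48 and Week 132. It concerns at most 201 RAJ1 subjects.

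Two stronger readings are not supported. One is that the end value will be at least 4.5 years old: that needs a RAJ1 subject treated for 84 months, and a tabulation band does not show that anyone reached it. The other is that every questionnaire needs a limit on the age of its end-of-treatment value: HAQ-DI, SF-36v2 and, for RAJ3/RAJ4 subjects, WPAI are still scheduled at end of treatment, and no comparable defect is shown for them.

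The analysis is descriptive, so what is at stake is the interpretation of one row.

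**What to change.** First establish, from the protocol versions and the collected data, whether FACIT-Fatigue was administered after ver. 1.3, and make Protocol Table 1, note n, 2.3.2, 5.3.1.8, 7.8.1(2) and 8.1.2 and the SAP agree.

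**If it was not:**
- In SAP 7.11.5(2) and Appendix 1 item 14, state the last visit at which FACIT was scheduled and end the by-visit table there. The Protocol synopsis makes ver. 2.0 and 3.0 effective centre by centre, so define this by the protocol version in force for the subject.
- For the End/discontinuation row, choose one of two rules. Either use only questionnaires completed at the end-of-treatment visit, without LOCF; or keep all subjects, label the row 'last available FACIT', and report time since assessment.
- Align the FACIT entry in Protocol 2.3.2.

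**If it was still collected:** add FACIT to Table 1, note n, 5.3.1.8 and the SAP schedule, and leave the analysis rows in place. Deleting the row before this is settled could discard valid long-term data.

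**Cost:** SAP wording, a matching protocol line and subject-level version dates; no new data. Under the first rule the row loses subjects and consists largely of those who stopped early, a selected group that the table should describe as such. The second rule keeps the numbers but needs the extra summary of elapsed time.
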